4.6. Safety Variables

4.6.1. Adverse Events, Serious Adverse Events

For safety variables, the following observation periods are defined:

- The pretreatment period is defined as the time from the signing of the ICF to before study drug administration.
- The EAP is defined as the day from first dose of study drug to day 169 ± 7 days
- The Follow-up period is defined as the end of the EAP to the end of the Follow-up Period (ie, the last study visit).

Treatment-emergent adverse events (TEAEs) are defined as those that are not present at baseline or represent the exacerbation of a pre-existing condition.

This study will collect data on the following targeted TEAEs: Grade ≥ 3 AEs, AEs leading to discontinuation, SAEs, grade ≥ 2 hypersensitivity reactions, and grade ≥ 3 injection-site reactions.

4.6.2. Adverse Events of Special Interest

Adverse Events of Special Interest (AESI) is defined as:

- Grade ≥ 2 hypersensitivity reactions
- Grade ≥ 3 injection-site reactions

4.6.3. Vital Signs and Laboratory Tests

Standard vital signs including body temperature, blood pressure, and heart rate, comprehensive vital sign assessment including additionally include SpO₂ and respiratory rate will be collected. Temperature and SpO₂ will be collected. Local safety laboratory tests collect absolute neutrophil count, platelet count, hemoglobin, ALT, AST, total bilirubin, and creatinine at baseline visit as well as study visits days 29,85 and 169.

4.7. Pharmacokinetic Variables

The pharmacokinetic variables are concentrations of casirivimab and imdevimab in serum and time. The sampling time points are specified in Table 1 of the protocol.

4.8. Immunogenicity Variables

The immunogenicity variables include ADA status, titer, and NAb status at nominal sampling time/visit. Serum samples for ADA will be collected at the clinic visits specified in the protocol SOE. Samples positive in the ADA assay will be further characterized for ADA titers and for the presence of NAb.

5. STATISTICAL METHODS

For continuous variables, descriptive statistics will include the following: the number of patients reflected in the calculation (n), mean, median, standard deviation, minimum, and maximum.

For categorical or ordinal data, frequencies and percentages will be displayed for each category.

5.1. Demographics and Baseline Characteristics

The variables for baseline characteristics include standard demography and other baseline summaries of efficacy variables will be displayed for each treatment group and all participant combined.

5.2. Medical History

Summary for each treatment group and all participant combined will be provided.

5.3. Prior/concomitant Medications

Prior /concomitant illnesses and medications will be summarized based on the safety population. Any treatment or procedure administered from the time of the first dose of study drug to the final study visit will be recorded as concomitant medication or concomitant procedure. This includes medications or procedures that were started before the study and are ongoing during the study.

Medications will be coded to the ATC level 2 (therapeutic main group) and ATC level 4 (chemical/therapeutic subgroup) and summarized Subjects will be counted once in all

ATC categories linked to the medication. Concomitant medications/procedures during EAP: medications taken or procedures performed in the period from the day of the first dose of study drug up to D176 or to the last visit if a subject discontinue from the study, whichever is earlier. This includes medications that were started before the initiation of study treatment and are ongoing during the EAP. Concomitant medications/procedures during the follow-up period: medications taken, or procedures performed from the day after the end of EAP to the final study visit or started during the treatment-emergent EAP and are ongoing after EAP.

5.4. Prohibited Medications if applicable

Prohibited medications will be summarized based on ITT under protocol deviations. Listing of prohibited medications described in the protocol will be provided for subjects under protocol deviations.

5.5. Subject Disposition

Subject study status will be summarized by treatment group and overall for the study.

The following will be provided:

- Number of screened subjects, defined as signed the ICF
- Number of randomized subjects
- Number of subjects randomized but who did not receive study treatment

- Number of subjects who discontinued the study, and the reasons for discontinuation
- A listing of subjects treated but not randomized, subjects randomized but not treated, and subjects randomized but not treated as randomized
- A listing of subjects prematurely discontinued from the study, along with reasons for Discontinuation
- A summary of analysis sets including randomized subjects and randomized subjects by treatment groups, ITT, mITT, SAF, PK, immunogenicity (AAS).

5.6. Extent of Study Treatment Exposure and Compliance

5.6.1. Measurement of Compliance

Participant treatment compliance in terms of total dose, number of doses, and number of SC injections will be summarized for each group. Compliance with study drug will be calculated as follows:

$$\text{Compliance (\%)} = 100 \times \frac{\text{Number of actual injections}}{\text{Number of planned injections}}.$$

This will be presented for SAF during EAP by each group and by all subjects combined.

5.6.2. Exposure to Investigational Product

The duration of study treatment exposure will be defined as day 1 through 4 weeks, ie, 28 days, after the last dose for a participant in the Q4W arms and day 1 through 12 weeks, ie, 84 days after the last dose for a participant in the Q12W arm. The duration of the study will be through the follow-up period defined as end of EAP through day 253 (± 14 days). Treatment exposure and study duration will be evaluated in the SAF.

5.7. Analyses of Efficacy Variables

The following null and alternate hypotheses will be tested for the primary endpoint unless otherwise specified:

H0: There is no treatment difference between REGN10933+REGN10987 and placebo

H1: There is a treatment difference between REGN10933+REGN10987 and placebo

Primary efficacy variable will be analyzed and compared between REGN-COV arms vs placebo.

5.7.1. Analysis of Primary Efficacy Endpoint

The mITT population will be the primary analysis population for efficacy. The ITT population will also be used for primary efficacy analysis. Participant data will be analyzed according to the group to which they were randomized.

The primary endpoint of the study is cumulative incidence of symptomatic (broad term), RT-PCR-confirmed SARS-CoV-2 infection cases during the efficacy assessment period (EAP). See Section 4.5.1 for the definition of a symptomatic SARS-CoV-2 infection.

The cumulative incidence of cases through the EAP will be estimated using the Kaplan-Meier method, and the antibody efficacy (AbE) will be estimated as the percent risk reduction (ie, $100 \times [1-HR]$, where HR is the hazard ratio for comparison of the incidence of cases in the antibody arm versus placebo). A unstratified Cox proportional hazard regression model with treatment group as a fixed effect, will be used to estimate the hazard ratio and 95% CI (2-sided). Nominal two-sided p-values will be reported for descriptive purpose using the log-rank test for pairwise comparison between each antibody arm and placebo.

For the primary analysis, cases will be counted from day 2 through day 176 (ie, day 169 +7 days), to allow for cases to accrue until the end of the EAP visit window per the Schedule of Events. Time of symptomatic SARS-CoV-2 infection will be the earlier of the sign/symptom onset date or the sample collection date for which RT-PCR result (local or central) was positive.

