### End-of-Study Visit

All participants, including those who do not consent to receive the optional final dose, will have a follow-up (end-of-study) telephone visit approximately 85 days (3 months) from their last dose of investigational drug (casirivimab+imdevimab or placebo) to monitor safety. Study assessments for the 3-month follow-up visit will be limited to the collection of targeted adverse events, as detailed in the new schedule of events (Table 2).

Sites will ensure that an additional discussion about the potential risks and benefits to the participant and fetus is discussed as part of re-consent for participants who become pregnant during the study.

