1.1. Background/Rationale

Study R10933-10987-COV-2176 was terminated early by the Sponsor due to the high frequency of the Omicron variant and reduced neutralization potency of casirivimab+imdevimab against the Omicron variant. The study is not being terminated due to any safety concerns, nor from any data obtained in this study. The protocol amendment 2 followed the sponsor's decision to close enrollment early and the study was revised to allow one optional dose and obtain final safety assessments.

Optional Dose

Casirivimab+imdevimab may continue to serve as an important pre-exposure prophylaxis therapeutic among immunocompromised individuals in regions where Omicron is not the dominant variant or in regions where Omicron prevalence subsides. For this reason, participants will have the option to receive a 1200 mg SC dose of casirivimab+imdevimab as a final study dose. This optional dose may be administered to all participants regardless of treatment assignment at randomization. However, participants will not be eligible to receive this dose if they have already received casirivimab+imdevimab as post-infection treatment.

Participants will be asked to return to the site for an unscheduled visit, during which they will be asked to consent to protocol amendment 2 and receive the final optional dose, if desired. This visit to receive the final optional dose should occur approximately 4 weeks after the most recent dose. Note that consent may be obtained remotely prior to this visit, if available and allowable by the study site.

Procedures in the Event of Suspected COVID-19

Participants with suspected COVID-19 may undergo an optional visit to evaluate symptoms by a study clinician (investigator or designee) and to undergo laboratory testing of SARS-CoV-2, as detailed in the new schedule of events (protocol amendment 2 Table 2). This optional visit

should occur as soon as possible (within 48 hours of symptom onset, if feasible). Note that clinician assessment of sign or symptoms may occur remotely. If remote assessment is performed, a confirmatory site visit for laboratory testing of SARS-CoV-2 can optionally occur after a clinician deems that the signs or symptoms are related to COVID-19.

Clinical Evaluation:

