Post-Infection Treatment. Participants with confirmed positive SARS-CoV-2 RT-PCR will be eligible for post-infection treatment (as described in protocol Section 6.4.4) at any time prior to receipt of the optional 1200mg SC dose (eg, during the 4 weeks between receipt of the last protocol-defined dose and optional 1200 mg SC dose). Once this optional dose has been

administered, post-infection treatment will no longer be offered. Likewise, any participant who receives post-infection treatment will not be eligible to receive the optional 1200 mg SC dose.

Participants with Positive SARS-COV-2 RT-PCR. Participants with a positive SARS-CoV-2 RT-PCR may have additional assessments and sample collections, including unscheduled visits every 7

days (± 1 day) for central laboratory RT-qPCR analysis until 2 consecutive negative test results are obtained:

- NP swab samples for RT-qPCR
- COVID-19 signs and symptoms evaluated by the investigator or designee
- Information regarding COVID-19-related medically-attended visits (MAVs; defined in protocol Section 9.2.4.3)

End-of-Study Visit

All participants, including those who do not consent to receive the optional final dose, will have a follow-up (end-of-study) telephone visit approximately 85 days (3 months) from their last dose of investigational drug (casirivimab+imdevimab or placebo) to monitor safety. Study assessments for the 3-month follow-up visit will be limited to the collection of targeted adverse events, as detailed in the new schedule of events (protocol amendment 2 Table 2).

Sites will ensure that an additional discussion about the potential risks and benefits to the participant and fetus is discussed as part of re-consent for participants who become pregnant during the study.

Analysis Plan

At the time that enrollment was closed, 66 participants had been enrolled in the study. Due to the early study closure and the resulting small sample size of enrolled participants, all analyses will be performed descriptively and only numeric comparisons will be performed. All safety endpoints (including AEs, TEAEs, AESIs, SAEs, and safety laboratory values) will be summarized. Selected efficacy, virology, PK, and/or immunogenicity data may also be analyzed descriptively. No interim analysis will be performed for this study, and no IDMC review meetings will occur.

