4.5. Efficacy Variable

4.5.1. Primary Efficacy Variable

Primary efficacy variable is cumulative incidence of symptomatic (broad term), RT-PCR-confirmed SARS-CoV-2 infection cases during the efficacy assessment period (EAP). The conditions for symptomatic SARS-CoV-2 infection are as follows:

- At least 1 sign or symptom (broad term definition) confirmed by a study clinician (investigator or designee) to be related to COVID-19, **and**
- A positive SARS-CoV-2 RT-PCR result (local or central analysis), **with**
- The sign/symptom onset date and the date of collection for the positive sample occurring within ± 7 days of one another

The primary endpoint will analyze symptomatic SARS-CoV-2 infection during the efficacy assessment period (EAP). The EAP is defined as the day 2 to day 169 +7 days . In addition, following rules will be applied to the primary analyses:

- Time to first symptomatic infection is defined as the first date of having either central or local lab determined positive test result.
- Subjects do not experience any symptomatic infection will be censored at last observed time point.
- Subjects who die at any time in the study or discontinue the study earlier (did not get any infections) will be censored at the end of study in case of final database lock.
- Subjects with COVID-19 symptoms that are missing a central lab determined RT-qPCR test during the EAP but have a positive SARS-CoV-2 test from a local lab will be considered as having a symptomatic infection if any of the symptoms occurred within 7 days of the positive SARS-CoV-2 test that was observed during the EAP.
- If subjects took optional dose of 1200mg, all the data after the dose will be removed from the efficacy analyses.

If subjects took investigational, authorized, or approved COVID-19 vaccines within 90 days of the last dose of study drug (or per current CDC recommendations) (CDC, 2021) or any covid-19 treatment medications for prevention after starting study treatment (Anti SARS-CoV-2 antibodies including Bamlanivimab/ Etesevimab, Casirivimab/ Imdevimab (REGEN-COV), Sotrovimab or Tixagevimab/ Cilgavimab (Evusheld); remdesivir; Nirmatrelvir/ Ritonavir (Paxlovid); Molnupiravir, all the efficacy data after these treatment will be removed from efficacy analyses.

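### The SAP keeps a Kaplan-Meier cumulative incidence to day 176 without restricting it to the follow-up that Amendment 2 and the optional-dose cut leave

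*SAP*

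**What the plan says.** SAP 5.7.1 keeps the protocol's horizon for the primary endpoint: "The cumulative incidence of cases through the EAP will be estimated using the Kaplan-Meier method". It then fixes the counting window: "For the primary analysis, cases will be counted from day 2 through day 176 (ie, day 169 +7 days". SAP 1.1 carries the same text. The window is justified by reference to the Schedule of Events, but SAP 10.1 (Table 3) and Protocol Table 1 both label that schedule as superseded by Amendment 2. The close-out schedule (SAP Table 4, Protocol Table 2) has no day-169 visit.

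Two other provisions shorten follow-up.

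- **Takers of the optional dose.** SAP 4.5.1: "If subjects took optional dose of 1200mg, all the data after the dose will be removed from the efficacy analyses". On timing, SAP 1.1 says: "This visit to receive the final optional dose should occur approximately 4 weeks after the most recent dose". On eligibility: "This optional dose may be administered to all participants regardless of treatment assignment at randomization". The exception is anyone already given casirivimab+imdevimab as post-infection treatment.
- **Decliners.** Their last contact is a telephone call "approximately 85 days (3 months) from their last dose of investigational drug (casirivimab+imdevimab or placebo) to monitor safety" (Protocol, End-of-Study Visit; same timing in SAP 1.1).

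SAP 4.5.1 also gives two censoring rules. Participants without a symptomatic infection are censored when last observed. Those who die or leave early without infection are censored at the end of study.

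SAP 1.2.4 lists one departure from the protocol, the dropping of some exploratory endpoints. The SAP contains no change of horizon, number-at-risk display or truncation rule.

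**The concern.** A cumulative incidence at a given day is only as good as the number still observed near that day. If an arm has nobody left, its Kaplan-Meier estimate at day 176 is either undefined or its last value carried forward. If a few are left, one late event moves the curve a long way: one case among 3 at risk is a step of up to 33 percentage points, against 1/16 = 6 points in a full arm of 16.

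On nominal timing, anyone left at day 176 declined the optional dose after five or six assigned doses, so the tail describes a self-selected group. Arms could also run out of follow-up on different days yet all be labelled with incidence through the EAP.

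The SAP was adapted to early closure elsewhere: an unstratified Cox model (5.7.1), no multiplicity adjustment (5.7.4), and region dropped from the model (6.5). The horizon was not.

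**Working it through.** **1. The plan's own figure.** End of the EAP visit window: 169 + 7 = day 176. It reproduces.

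**2. Where efficacy follow-up ends.** Dosing in all arms is every 4 weeks, with six administrations (Protocol 3.2.2 and 8.1), so dose *k* falls on day 1 + 28(*k* − 1). Windows are from Protocol Table 2: ±7 days for the optional dose, ±14 for the final call.

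- Taker: efficacy data end at 1 + 28(*k* − 1) + 28.
- Decliner: last contact at 1 + 28(*k* − 1) + 85.

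| Assigned doses received | Last dose (day) | Taker ends (window) | Decliner ends (window) |
|---|---|---|---|
| 1 | 1 | 29 (22–36) | 86 (72–100) |
| 2 | 29 | 57 (50–64) | 114 (100–128) |
| 3 | 57 | 85 (78–92) | 142 (128–156) |
| 4 | 85 | 113 (106–120) | 170 (156–184) |
| 5 | 113 | 141 (134–148) | 198 (184–212) |
| 6 | 141 | 169 (162–176) | 226 (212–240) |

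Nominally no taker reaches day 176. A six-dose taker does so only at the window limit or if dosed late. Decliners with three or fewer doses cannot reach even day 169. This step needs no calendar dates.

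**3. How many remain.** This does need dates. Given: enrolment closed 16 Dec 2021 (SAP 1) with 66 randomized (SAP 2.1). Not given, so assumed:

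- First enrolment: 21 Oct 2021 (site memorandum date) or 10 Sep 2021 (latest access date in the protocol's references), with uniform accrual to closure.
- Amendment 2 takes effect on date *A*, with assigned doses on schedule until then.
- Optional-dose uptake *u* of 0%, 50% or 100%.

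Doses received: *k* = min(6, floor((*A* − enrolment date)/28) + 1). Someone who had finished six doses before *A* takes the optional dose no earlier than *A*. Count = 66 × [*u* × share of takers still in + (1 − *u*) × share of decliners still in].

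Example: start 21 Oct, *A* = 28 Feb 2022. Five doses require enrolment by 28 Feb − 112 days = 8 Nov, which is 19 of the 57 accrual days. Decliners reaching day 176: 66 × 19/57 = 22. At 50% uptake: 11, under three per arm.

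Number of 66 still in, at uptake 0% / 50% / 100%:

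| Start | Amendment 2 effective | At day 169 | At day 176 |
|---|---|---|---|
| 21 Oct | 31 Jan 2022 | 22.0 / 11.0 / 0 | 0 / 0 / 0 |
| 21 Oct | 28 Feb 2022 | 54.4 / 27.2 / 0 | 22.0 / 11.0 / 0 |
| 21 Oct | 31 Mar 2022 | 66 / 45.7 / 25.5 | 57.9 / 28.9 / 0 |
| 21 Oct | 30 Apr 2022 | 66 / 63.1 / 60.2 | 66 / 42.8 / 19.7 |
| 10 Sep | 31 Jan 2022 | 40.4 / 21.6 / 2.7 | 21.6 / 10.8 / 0 |
| 10 Sep | 28 Feb 2022 | 59.3 / 40.4 / 21.6 | 40.4 / 20.2 / 0 |
| 10 Sep | 31 Mar 2022 | 66 / 54.2 / 42.4 | 61.3 / 40.1 / 18.9 |
| 10 Sep | 30 Apr 2022 | 66 / 64.3 / 62.6 | 66 / 52.5 / 39.1 |

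These counts use nominal visit timing and ignore infections, withdrawals and mITT exclusions. Protocol 9.1.2 also makes COVID-19 assessment optional after Amendment 2, so being in the study is not the same as being assessed.

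**4. Expected cases.** The Protocol Table 6 rates reproduce from 1 − (1 − 0.0402)^HR: 4.02% on placebo, then 1.628%, 1.829% and 2.231% at HR 0.40, 0.45 and 0.55. With 66/4 = 16.5 per arm followed for the full 6 months: 16.5 × (0.0402 + 0.01628 + 0.01829 + 0.02231) = 1.6 cases, of which 0.66 on placebo.

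**5. Censoring rules.** For someone who leaves early without infection, the two SAP 4.5.1 rules give different censoring days. Read literally, censoring at the end of study keeps that person in the risk set after observation has stopped, so a printed number at risk could look adequate when it is padded.

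**The case against.** The strongest reply is that little depends on this curve. SAP 1 says the objectives could not be achieved and treats every endpoint as exploratory; SAP 1.1 makes all analyses descriptive. The efficacy measure is 100 × (1 − HR) from a Cox model with nominal log-rank p-values. Both use the risk sets at event times and need nobody at risk on day 176. Kaplan-Meier itself allows staggered censoring, and day 176 can be read as a counting window, since 5.7.1 does not ask for a day-176 table. With 1.6 expected cases, nobody would over-read the result.

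Most of that stands. The Cox and log-rank analyses remain usable, subject to the usual requirement that censoring be non-informative, and the exploratory label lowers the stakes. It does not dispose of the point: 5.7.1 still calls for cumulative incidence through the EAP, without any condition that the data reach that far.

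A reader might also infer that most or all participants stop early and that few or none are at risk at day 176. The documents do not support that. It turns on an Amendment 2 date and an uptake that they do not give, and a spring 2022 date or low uptake leaves many at risk. The choice of day matters too: with a 21 Oct start, Amendment 2 on 31 Jan and 50% uptake, 11 remain at day 169 and none at day 176. Visit windows blur that boundary further.

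**Conclusion.** The concern holds as a limited one. The SAP retains a 6-month cumulative incidence tied to a withdrawn schedule, while its own data cut ends every on-schedule taker's efficacy follow-up by day 169. Decliners with four or fewer doses nominally end by day 170. That part rests only on the documents' visit arithmetic.

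The number at risk at day 176 is unknown: 0 to 66 of 66 over the assumed enrolment starts, Amendment 2 dates and uptake. It is 0 at any uptake if enrolment began on 21 Oct 2021 and Amendment 2 took effect by 31 Jan 2022. It is 66 at zero uptake with an effective date of 30 Apr 2022.

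It would be wrong to conclude that the primary analysis as a whole is invalid. What is unsupported is one figure, the 6-month incidence by arm, in a descriptive analysis. It should still be corrected. The SAP was approved on 17–18 June 2022; a participant enrolled on 16 Dec 2021 reached day 176 on 9 June 2022, so a supportable horizon could have been set from pooled follow-up.

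**What to change.** In SAP 5.7.1, and in the copy in SAP 1.1:

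- Report Kaplan-Meier curves with numbers at risk by arm.
- Truncate all curves at one common day, chosen from pooled follow-up without reference to arm outcomes.
- Report a day-169 or day-176 incidence only if a pre-stated minimum per arm is still under observation. The minimum (5, for instance) and the display days are the sponsor's choice, but should be fixed before outcomes by arm are seen.
- Add cases and person-days at risk per arm, with an exact Poisson 95% CI for the rate.

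In SAP 4.5.1, first reconcile the two censoring rules so that early discontinuers are censored at their last observation; otherwise the numbers at risk cannot be trusted. Record the change of horizon in SAP 1.2.4.

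The cost is SAP wording and one extra table, with no new data or participants. The downside is that the reported incidence may cover less than the protocol's 6 months. If enough participants did reach day 176, the rule still allows that figure to be reported.

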1. OVERVIEW

This is a randomized, double-blind, placebo-controlled, phase 3 study to assess the safety and efficacy of anti-SARS-CoV-2 mAb therapy, casirivimab+imdevimab as pre-exposure prophylaxis against symptomatic COVID-19 in immunocompromised individuals, defined according to the primary and secondary immunodeficiencies outlined in the study eligibility criteria.

Regeneron decided to close enrollment of the COV-2176 Study on Dec 16 2021. This was based on several factors, including the recent Emergency Use Authorization of an alternative therapy in pre-exposure prophylaxis as well as emerging evidence surrounding Variants of Concern (VOC). While casirivimab+imdevimab retains activity against other known VOCs, including Delta, which was the most prevalent variant in the U.S., it has diminished potency against Omicron. Consequently, Regeneron stopped recruitment into this study.

As a result of the early termination of the study, the objectives could not be achieved and none of the hypotheses are evaluable. Although this SAP refers to primary and secondary endpoints and objectives based on their description in the protocol, these have all been designated exploratory due to the early termination.

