1. Have tested negative by RT-qPCR (central lab results), and
2. Have central serology test result (ElecSys® anti-S RBD total Ig) ≤ 50 U/mL

Participants who are deemed medically ineligible or contraindicated to receiving a full course of standard-of-care COVID-19 vaccine will also be included in the mITT.

Primary Efficacy Analysis

The EAP is defined as the day 2 to day 169 visit. The cumulative incidence of cases through the EAP will be estimated using the Kaplan-Meier method, and the antibody efficacy (AbE) will be estimated as the percent risk reduction (ie, $100 \times [1-\text{HR}]$, where HR is the hazard ratio for comparison of the incidence of cases in the antibody arm versus placebo). A unstratified Cox

proportional hazard regression model with treatment group as a fixed effect will be used to estimate the hazard ratio and 95% CI (2-sided).

For the primary analysis, cases will be counted from day 2 through day 176 (ie, day 169 + 7 days), to allow for cases to accrue until the end of the EAP visit window per the Schedule of Events. Time of symptomatic SARS-CoV-2 infection will be the earlier of the sign/symptom onset date or the sample collection date for which RT-PCR result (local or central) was positive.

Safety Analyses

For safety variables, the following observation periods are defined:

The pretreatment period is defined as the time from the signing of the ICF to before study drug administration.

The EAP is defined as the day from first dose of study drug to day 169 ± 7 days

The Follow-up period is defined as the end of the EAP to the end of the Follow-up Period (ie, the last study visit).

Treatment-emergent adverse events (TEAEs) are defined as those that are not present at baseline or represent the exacerbation of a pre-existing condition.

Per protocol amendment 2, this study will collect all clinical and laboratory TEAEs that are not related to the patient's underlying (non-COVID) disease and/or not related to treatments for the underlying conditions.

Other Safety Analyses

Vital Signs, Laboratory Tests, treatment exposure, and treatment compliance analyses will be performed.

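### SAP 5.7.1 plans a Cox hazard ratio and antibody efficacy with 16–17 participants per arm but has no rule for an arm without cases

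*SAP*

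**What the plan says.** - **Comparison.** SAP 5.7.1: "A unstratified Cox proportional hazard regression model with treatment group as a fixed effect, will be used to estimate the hazard ratio", with a two-sided 95% CI and AbE = 100 × (1 − HR). SAP 1.1 repeats this. The type of interval is not named.
- **Per-arm estimate.** SAP 5.7.1: "The cumulative incidence of cases through the EAP will be estimated using the Kaplan-Meier method".
- **p-values.** SAP 5.7.1: "Nominal two-sided p-values will be reported for descriptive purpose using the log-rank test", for each antibody arm against placebo. SAP 5.7.4 makes no multiplicity adjustment.
- **Sample.** SAP 2.1 gives 66 randomised, about 16–17 per arm.
- **Status.** SAP 1 says that "the objectives could not be achieved and none of the hypotheses are evaluable". SAP 1.1 and the statistical paragraph of Protocol Amendment 2 say that "all analyses will be performed descriptively and only numeric comparisons will be performed". SAP 5.7 still reads: "The following null and alternate hypotheses will be tested for the primary endpoint unless otherwise specified".
- **Censoring.** SAP 4.5.1 says: "Subjects do not experience any symptomatic infection will be censored at last observed time point". Its next rule censors infection-free participants who die or leave early at the end of the study instead. It also removes efficacy data after the optional dose, a COVID-19 vaccine or other listed treatments.

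I found no rule for an arm with no cases. SAP 4.5.1 covers censoring and data removal, 6.2 only points back to 5.7, 6.3 covers dosing dates, adverse events and medications, and 6.6 is a heading without text in the public copy.

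**The concern.** This SAP was written after termination and was partly adapted to the small sample: the protocol's stratified Cox model became unstratified. The HR, AbE and interval remained, with nothing said about the outcome that is commonest at the planning rates, a pair in which at least one arm has no cases. If the antibody arm has none, the HR estimate runs to 0 and AbE to 100%. If placebo has none, the HR is infinite. If neither has any, there is no HR. How such rows are shown would then be settled by programming defaults or after the data are seen, and a reader of the tables could take an AbE of 100% from 16–17 participants per arm at face value.

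The censoring rules matter for the same tables. Protocol 6.6 defines end of study by the last participant. On that definition the second rule in SAP 4.5.1 credits people who left early with time in which nobody observed them. This lowers any incidence rate and affects the Kaplan-Meier curve.

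**Working it through.** **Inputs.** Placebo incidence p0 = 4.02% over 6 months (Protocol 11.2). HR = 1 − AbE = 0.40, 0.45 and 0.55 for arms 1, 2 and 3 (Protocol Table 6; the text of Protocol 11.1 swaps the last two HR labels). n = 16 or 17 per arm (SAP 2.1). The 10% and 20% incidences and HR 1 are assumptions.

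**The plan's own figures reproduce.** 1 − (1 − 0.0402)^HR gives 1.628%, 1.829% and 2.231%, as in Table 6. Schoenfeld power at one-sided 0.025 with 108, 112 and 120 pairwise cases is 99.7%, 98.8% and 90.6%. Simulated with the four interim looks it is 99.7%, 98.7% and 90.1%, against 99.7%, 98.7% and 90% stated. With 2188 × 0.9 per arm and 5% dropout, expected cases total 186.4 against 186. The planning rates are therefore a sound starting point.

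**Probability of no cases.** With follow-up fraction f (1 = 6 months):
- placebo: P0 = (1 − p0)^(f·n)
- antibody: Pa = (1 − p0)^(f·HR·n)
- at least one arm of the pair without cases: 1 − (1 − P0)(1 − Pa)
- AbE 100%: (1 − P0)·Pa; HR infinite: P0·(1 − Pa); no case in either arm: P0·Pa

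Example, n = 16, HR 0.40: P0 = 0.9598^16 = 0.519 and Pa = 0.9598^6.4 = 0.769, so 1 − 0.481 × 0.231 = 0.889. For n = 17, HR 0.55: P0 = 0.498, Pa = 0.681, giving 0.840.

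| Placebo incidence | Follow-up | HR 0.40–0.55 | HR 1 |
|---|---|---|---|
| 4.02% | full | 84–89% | 75–77% |
| 4.02% | half | 95–97% | 91–92% |
| 10% (assumed) | full | 48–60% | 31–34% |
| 20% (assumed) | full | 14–26% | about 5% |
| 20% (assumed) | half | 45–58% | 28–31% |

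At 4.02% and full follow-up, the split is:
- HR 0.40–0.55: AbE 100% in 34–38%, HR infinite in 12–16%, no case in either arm in 34–40%.
- HR 1: 25%, 25% and 25–27%.

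The three comparisons share one placebo arm. At the planning rates all three HRs are finite in about 1% of trials. About 1.6 cases are expected in the whole study, and none at all in 19–21%. With 14–15 per arm, allowing for the protocol's 10% loss to the mITT set, the 84–89% becomes 87–91%.

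**What the software does.** A Cox fit to an illustrative 0 of 17 against 2 of 16 gave a log HR of about −112 with a standard error of about 10^24, so the Wald interval is useless.

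**What still works.** The exact Poisson 95% upper limit at zero cases is −ln(0.025) = 3.689 events. Sixteen participants over days 2–176 give 16 × 175 = 2,800 person-days, and 3.689/2,800 = 1.32 per 1,000. For comparison, the planning placebo rate is −ln(0.9598)/175 = 0.23 per 1,000, so the interval is valid but wide.

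**Effect of the censoring rule (illustration).** Suppose 4 of 16 leave event-free at day 57, with 56 days each from day 2. Last-observation censoring gives 12 × 175 + 4 × 56 = 2,324 person-days and an upper limit of 1.59 per 1,000. End-of-study censoring gives 2,800 and 1.32, which is 20.5% more person-time. With 1 of 16 leaving, the excess is 4.4% (2,681 against 2,800).

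**The case against.** The strongest reply is that nothing depends on these rows. The SAP designates everything exploratory, labels the p-values nominal, makes no multiplicity adjustment and keeps the Kaplan-Meier estimate, which is defined at zero cases. All of that stands, and it is why the point is minor. The planning rates may also not describe this trial, which closed as Omicron spread. That stands too. Higher incidence lowers the probabilities, while shorter follow-up, which SAP 4.5.1 makes likely by removing data after the optional dose, raises them.

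Four stronger readings are tempting, and the documents do not support them:
- **The plan leans towards a false efficacy result.** With no drug effect, AbE of 100% and an infinite HR are equally likely at every incidence. The excess of AbE 100% at the planning rates reflects the efficacy assumed there.
- **No interval exists at zero cases.** That is true only of the HR, and only when neither arm has a case. With 0 antibody cases against 1, 2 or 3 placebo cases (16 per arm), a profile-likelihood upper limit for the HR would be 5.83, 1.56 or 0.84. The SAP does not specify that method.
- **The HR and AbE must go, or need a minimum case count.** Protocol 11.4.3.1 specifies them, and a rule for the zero-case situation closes the gap.
- **The SAP plans a confirmatory test.** The sentence in SAP 5.7 carries an exception clause, and SAP 1, 1.1, 5.7.1 and 5.7.4 all say otherwise. It is leftover wording.

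**Conclusion.** Minor, and it holds. With 16–17 per arm, the HR, AbE and Wald interval in SAP 5.7.1 have no finite estimate in 84–89% of comparisons at the planning rates and in 75–77% with no drug effect. The SAP gives no fallback. These figures assume exponential event times, full 6-month follow-up and the randomised numbers per arm; the table shows how far other incidences and shorter follow-up move them. The actual incidence and HR are not in the documents. The two censoring rules in SAP 4.5.1 also conflict, and the choice changes the person-time. The conflict between SAP 5.7 and the descriptive-only statements is editorial. No trial decision changes.

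**What to change.** 1. In SAP 5.7.1 and 1.1, report per arm the number of cases, person-days at risk and incidence rate with an exact Poisson 95% CI, beside the Kaplan-Meier estimate.
2. State, before database lock, that HR, AbE, CI and the nominal p-value are printed as 'not estimable' whenever either arm of the pair has no cases. The log-rank p-value is strictly undefined only when neither arm has a case; withholding it with the HR keeps each row consistent.
3. In SAP 4.5.1, use one censoring rule: event-free participants who die or discontinue are censored at their last observed time point. End person-time where 4.5.1 already removes data. Apply the same rule to the Kaplan-Meier estimate.
4. Delete the H0/H1 testing text in SAP 5.7.
5. Record these changes in SAP 1.2.4.

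The cost is SAP wording and simple programming. The exact intervals will be wide and will not show efficacy.
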